#### Analytic Plan

A [mixed]-effects general linear model (GLM) will test

[figure not shown]
the test the prediction that the high polygenic risk group will select louder noise blasts after alcohol

**Figure 6. Anticipated results comparing polygenic risk groups on their aggressive behavior, after alcohol or placebo.**

[figure not shown]

the task. Multiple comparisons corrections will be conducted using nonparametric threshold-free cluster enhancement. Mediation models will then be fit in which the effect of polygenic risk score group on aggression (after the alcohol administration) will be mediated by functional and structural brain estimates from brain regions that were significantly different between the two polygenic risk groups (Figure 8). The PROCESS macro for SPSS will be used to conduct nonparametric bootstrapping (using 5,000 bootstrapped resamples) to test the significance of each neural mechanism's indirect effect.

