## SPECIFIC AIMS

Aggressive behavior in the context of alcohol misuse is a substantial public health concern. Genetic predispositions have been identified for both aggression and alcohol misuse. However, the biological factors that predispose individuals towards alcohol-influenced aggression remain poorly understood. Specifically, the extent to which alcohol-influenced aggression is genetically-influenced is unknown. Further, it remains to be seen whether alcohol-influenced aggression is uniquely heritable, or is simply the by-product of genetic risk factors for both alcohol misuse and aggression. If alcohol-influenced aggression is found to be substantially genetically-influenced, the specific genetic and neural pathways through which these effects are transmitted must then be investigated. The goal of the research activities in this K01 proposal is to fill these gaps in our knowledge.

[figure not shown]
The overall objective of the research activities in this K01 award proposal is to examine the genetic factors and neural mechanisms that promote alcohol-influenced aggression. The proposed research activities will address the following research aims and test their associated hypotheses:

**Aim 1: Examine the extent to which genetic factors influence the extent to which individuals act aggressively in the context of alcohol misuse.** *Hypothesis 1:* Genome-wide complex trait analysis (GCTA) will reveal that alcohol-influenced aggression exhibits substantial genetic heritability.

**Aim 2: Examine whether genetic factors for alcohol-influenced aggression exist above-and-beyond genetic risk factors for general aggressiveness and alcohol misuse.** *Hypothesis 2:* After statistically controlling for genome-wide associations with non-alcohol-influenced aggression and alcohol misuse, significant genetic heritability will still be observed for alcohol-influenced aggression via GCTA.

**Aim 3: Identify the specific genetic loci and polymorphisms that are most strongly linked to alcohol-influenced aggression and create polygenic risk scores from these findings.** *Hypothesis 3:* Genome-wide association study (GWAS) techniques will identify specific gene polymorphisms associated with alcohol-influenced aggression.

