**Aim 4: Identify functional and structural brain mechanisms that transmit the genetic effects on alcohol-influenced aggression.** *Hypothesis 4:* Polygenic risk scores for alcohol-influenced aggression will be associated with greater laboratory aggression, through changes in brain structure and function.

This proposal capitalizes on the resources available through [NIH-funded publicly-available datasets from the database of Genotypes and Phenotypes (dbGaP)] and VCU's Spit for Science (S4S) project, on which my primary mentor, [name] is a Principal Investigator. Drs. [name] and [name] (Co-Mentors) also play substantial roles in many of these projects. I would begin by analyzing existing data from [the dbGaP discovery sample], then seeking to replicate these findings with ongoing data collection for Spit for Science at my current institution, VCU. Finally, I would conduct a new MRI brain imaging study, using S4S participants (recruited based on their underlying genetic risk profiles) analyses in order to leverage my existing skillset in neuroimaging and laboratory aggression measurement and further accomplish the proposed research aims.

Accomplishing these aims would advance my long-term goal to become an independent alcohol investigator who integrates across multiple disciplines to study the factors that influence alcohol-influenced aggression. These activities would set the stage for R01-level applications to investigate the environmental factors that influence these effects, and biologically-informed interventions that might ameliorate them.

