**Table 2. Demographics of dbGaP projects used in discovery sample.**

Project	Sex	Age Range	Age M(SD)	Ethnicity/Race
ADGWAS	46.9% F, 53.1% M	18-79	37.4 (11.8)	35.1% ED, 64.9% EM
COGA	53.7% F, 46.3% M	18-97	39.83 (14.6)	65.8% ED, 26.2% EM
COGEND	61.8% F, 38.2% M	25-47	36.5 (5.5)	55.4% ED, 44.6% EM
FSCD	50.3% F, 49.7% M	18-60	37.0 (8.8)	48.3% ED, 51.7% EM
GWASHD	47.0% F, 53.0% M	18-58	35.6 (9.2)	100% ED

ED=European-Descent, EM=Ethnic-Minority

Genotyping and imputation. Participants provided blood samples to biologic repositories, on which whole-genome genotyping was performed. Several genome-wide Illumina arrays were used, including the Human OmniExpress 12.VI, the Omni2.5 BeadChip, and the Human610-Quad BeadChip.] Genotypic data were checked for minor allele frequency (SNPs excluded with frequencies < 3%), pedigree structure/Mendelian inconsistencies, with samples imputed to 1000 Genomes using SHAPEIT and then IMPUTE2.

[figure not shown]
Phenotype measures. Participants completed the Semi-Structured Assessment for the Genetics of Alcoholism (SSAGA) [or variants of this instrument (e.g., Semi Structured Assessment for Drug Dependence and Alcoholism) that included our specific questions-of-interest]. The SSAGA includes reports of whether participants have previously performed physically-aggressive acts, and whether the acts were performed while participants had consumed alcohol or not (e.g., “have you ever physically injured anyone on purpose?”). Greater alcohol-influenced aggression is indicated by a greater number of yes (with alcohol) responses to such questions and non-alcohol-influenced aggression is indicated by a greater number of yes (no alcohol) responses. The SSAGA also assesses the extent to which participants have previously engaged in specific aspects of alcohol misuse (e.g., binge drinking).

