**Figure 2. Competing conceptual models of the heritability of alcohol-influenced aggression.**

aggression, and alcohol misuse. Fixed-effects covariates will include age, ethnicity/race, sex, and socioeconomic status. To prevent heritability inflation, any two participants who share a second-cousin degree of relatedness or more will be excluded from subsequent analyses. A heritability ( $h^2$ ) estimate will be calculated for alcohol-influenced aggression, *controlling* for the heritability of non-alcohol-influenced aggression and alcohol misuse phenotypes. A substantial heritability estimate ( $h^2 > 0.1$ ,  $p < .05$ ) for alcohol-influenced aggression will serve as support for the unique genetic basis for this phenotype.

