**Genome-wide association study (GWAS).** After the GCTA, GWAS will be used to identify single nucleotide polymorphisms (SNPs) and clusters of SNPs that are significantly associated with alcohol-influenced aggression. Due to the skewness of the alcohol-influenced aggression scores (see Figure 3), quasi-Poisson regression analyses will be used to accommodate such a distribution using the Bioconductor v2.1 package and SNPTEST v2.5. Specifically, alcohol-influenced aggression scores will be regressed onto principal components of the available SNPs using an additive model, excluding non-autosomal SNPs, with demographics factors as covariates. Due to racial stratification, separate GWAS will be performed for participants of African, American, East Asian, European, South Asian, and Mixed Race descent. Participants will be empirically assigned to these ancestral super-populations using the 1KGP population base and the Mahalanobis' distance between each population. I will meta-analyze these separate sets of GWAS findings METAL v3.0^32, which will produce meta-analytic '% variance explained' effect size estimates and  $p$  values for each SNP. [In addition to this meta-analytic approach, I will test for gene-by-race/ethnicity moderation using a kernel-machine approach to estimate whether each SNP's association with alcohol-influenced aggression varies across the discovery sample's diverse racial/ethnic groups, using the Robust Joint Tests package.] After correction for genetic inflation and weighting based on sample size, I will calculate polygenic risk scores for alcohol-influenced aggression [based on SNPs meeting increasingly stringent significance thresholds: .5, .4, .3, .2, .1, .05, .01, .001, .0001. The threshold that maximizes the variance explained ( $R^2$ ) in alcohol-related aggression will be used for risk score calculation.] Using an additive approach, I will sum across the number of alleles that are significantly linked to the phenotype, weighted by their respective effect size estimates from the GWAS. For example, if the A allele (versus the corresponding G allele) of a given SNP is significantly associated with greater alcohol-influenced aggression, then each copy of the A allele will be initially coded as +1 (GG = 0, GA = 1, AA = 2). These scores will then be multiplied by the GWAS effect size estimate for that given SNP. This polygenic risk scores will capture aggregate genetic risk for alcohol-influenced aggression in a manner that represents the current state of the field.

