MRI [Sessions]. [The MRI study will take the form of a two-session experiment, in which alcohol or placebo beverages are administered to each participant in a counterbalanced order. In Session 1,] participants will arrive at VCU's Collaborative Advanced Research Imaging (CARI) facility where they will repeat the screening procedures and then will practice the computer tasks that they will perform in the scanner. Then, participants will be told that they will receive [either] a placebo [or] an alcoholic beverage, but that they will not be informed of the nature of each beverage until the end of the study (see Figure 4 for the MRI scan timeline). [By random assignment,] participants will then consume [either a placebo beverage of orange juice with 4ml ethyl alcohol added to the rim or an alcoholic beverage

consisting of a 1:5 ratio of 95% ethyl alcohol and orange juice. The alcohol dose will be proportional to participants' body weight and sex, due to sex differences in body fat composition and alcohol metabolism (females: 0.9 g/kg ethyl alcohol; males: 1.0 g/kg ethyl alcohol). This alcohol dose typically increases participants' breath-alcohol-concentration to .08%, the legal driving limit in Virginia.] After consuming the beverage, participants will then be placed in the MRI scanner and complete a validated laboratory aggression paradigm that allows individuals to "hurt" a fictitious opponent with an aversive noise blast, while undergoing echo-planar functional MRI (EPI). In this task, participants compete against an opponent to press a button faster, and the loser of the competition then hears an aversive noise blast. Aggression is operationalized as the

Figure 4. Timeline of both MRI sessions.

volume of the noise blast (65-105 decibels) that participants select for a fictional opponent who repeatedly provokes them by selecting extremely loud noise blasts. After completing these scans, [participants will leave and return to the CARI center 7 days later for Session 2. Participants will consume either a placebo (if they consumed an alcoholic beverage in Session 1) or an alcoholic beverage (if they consumed an alcoholic beverage in Session 1), and then will be returned to the scanner to complete the aggression paradigm a second time against a new provocative opponent.] Participants will be told that both of their opponents are same-sex VCU undergraduates, when in fact, they are computer programs.

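### The Phase II mediation outcome is aggression after alcohol only; an alcohol-specific mechanism under Aim 4 needs a pre-specified alcohol-versus-placebo contrast

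*Combined protocol and SAP*

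**What the plan says.** Aim 4 (Specific Aims) is to identify "functional and structural brain mechanisms that transmit the genetic effects on alcohol-influenced aggression". Hypothesis 4 is less demanding: the risk scores "will be associated with greater laboratory aggression, through changes in brain structure and function", with no comparison between beverages.

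Under MRI Sessions (Phase II), "alcohol or placebo beverages are administered to each participant in a counterbalanced order", and the same noise-blast task is done in both sessions.

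The Phase II Analytic Plan then describes mediation models in which "the effect of polygenic risk score group on aggression (after the alcohol administration) will be mediated by functional and structural brain estimates". Mediators are taken from regions that differ between the two risk groups; that sentence has no beverage term. The Phase II power paragraph gives 99 per group for 80% power and also mentions no beverage contrast.

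The caption of Figure 6 indicates that the behavioural comparison covers both beverages. The text just before the mediation sentence is broken, and Figures 4, 6 and 8 are not available.

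**The concern.** The plan treats alcohol-influenced and general aggression as things to be told apart. The Specific Aims ask whether the phenotype is "simply the by-product of genetic risk factors for both alcohol misuse and aggression", and the GCTA estimate is to be controlled "for the heritability of non-alcohol-influenced aggression and alcohol misuse phenotypes".

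That control is not stated at the next two steps. The GWAS that produces the risk score is described as "excluding non-autosomal SNPs, with demographics factors as covariates", with no mention of adjustment for non-alcohol aggression. The mediation outcome is the alcohol session alone. A score that partly carries general aggressiveness could therefore act through a general-aggression circuit and still give a significant indirect effect. Aim 4 could not then say which kind of mechanism had been found.

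The behavioural group-by-beverage test does not fill the gap. It tests the total effect of risk group, not the part that runs through the brain measure.

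**Working it through.** **The plan's own figure.** 198 + 4 = 202 reproduces. The 198 itself cannot be rebuilt: the path coefficients, alpha and sidedness are not given, and the indirect effect of 0.09% has no stated scale. The effect sizes below are therefore assumptions.

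**Inputs.** From the plan: 99 per group, n = 198. Assumed: alpha .05 two-sided; standardised paths a (group to brain) and b (brain to alcohol-session aggression), a = b = .23, chosen to give roughly the claimed 80% power; correlation r between the two sessions' aggression scores of .3, .5 or .7; a mediator with one value per person, such as a structural measure.

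**Method.** An indirect effect counts as significant when both paths are (joint-significance test). There were 20,000 simulated trials per cell, with session order as a covariate in the difference model. A general pathway has the same b after both beverages, an alcohol-specific one has b = 0 after placebo, and a half-specific one has .115 after placebo.

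**Hand check, alcohol-session outcome.**
- SE(a) = √[(1 − .23²)/198] = .0692, so z = 3.33 and power = .914.
- SE(b) = √[(1 − .23²)/(198 × (1 − .23²))] = .0711, so z = 3.24 and power = .899.
- Product: .914 × .899 = .82. The placebo path does not appear in it, so the result is the same for every kind of pathway.

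**Hand check, difference outcome.** The variance of the difference is 2(1 − r), and its slope on the mediator, b_D, is the alcohol b minus the placebo b. SE(b_D) = √[(2(1 − r) − b_D²)/(198 × (1 − .23²))].
- General: b_D = 0, giving .914 × .05 = .046.
- Alcohol-specific: b_D = .23; SE = .0848, .0711 and .0540, giving .71, .82 and .90.
- Half-specific: b_D = .115, giving .24, .32 and .49.

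**Simulated percentage significant (r = .3 / .5 / .7).**

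| Pathway | Alcohol session | Difference | Both |
|---|---|---|---|
| General | 81 / 81 / 81 | 5 / 4 / 5 | 4 / 3 / 4 |
| Half-specific | 81 / 81 / 81 | 24 / 31 / 48 | 23 / 30 / 45 |
| Alcohol-specific | 82 / 81 / 81 | 69 / 81 / 90 | 65 / 74 / 80 |

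For a = b from .20 to .30, the alcohol-session test gives 64–98% for either pathway; the contrast gives 4–5% (general) against 52–99% (specific). A percentile bootstrap with other effect sizes (group difference on the mediator of 0.4 to 0.6 SD, b = .3, residual session correlation .5) gives 79–97% for the alcohol-session test and 4–5% for the contrast under a general pathway.

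**Does the behavioural test help?** Take a general brain path plus an alcohol-specific direct group effect of .2 that bypasses the brain measure. The alcohol-session mediation and the group-by-beverage test are both significant in 55 / 67 / 80% of trials, the contrast mediation in 4%. For a purely mediated alcohol-specific pathway, the group-by-beverage effect is only .23 × .23 = .053. The group-by-beverage test then detects it in about 10–16% of trials.

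**Alternatives that fail.** With a general pathway, adjusting alcohol-session aggression for the placebo score is still significant in 60 / 43 / 25% of trials. An alcohol-session-only fMRI mediator paired with the difference outcome is significant in 54% (mediator correlation .3) and 31% (.5).

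**fMRI mediators measured in both sessions.** Bootstrapping the difference between the two sessions' indirect effects gives 4–6% for a general pathway, 56–75% when the a-path is alcohol-specific and 50–68% when the b-path is.

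**The case against.** The strongest reply is that no error is shown. The stated model tests Hypothesis 4, and it matches the discovery phenotype: "Greater alcohol-influenced aggression is indicated by a greater number of yes (with alcohol) responses". Aim 4 does not itself say that the mechanism must be absent after placebo; the distinct-from-general question is put under Aim 2. The Summary and Future Directions section already describes the Phase II result as concerning responses after alcohol. All of this is correct. It is why the Hypothesis 4 test should stay as it is and why the point concerns only what may be claimed under Aim 4.

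Second, decisive text is lost. The mediators may already be alcohol-versus-placebo contrasts, and Figure 8 may show more than the text does. This limits the point, but the outcome named in the readable sentence is the alcohol session.

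Third, the numbers are illustrative. The .23 was chosen to match the claimed power, and a null contrast rejects at about 5% by construction. The direct effect of .2 is nearly four times the mediated .053; without it, a general pathway passes both the mediation and the group-by-beverage test in only about 4% of trials. The simulation also ignores the selection of regions that differ between groups. These objections affect the size of particular cells. They do not affect the reason the stated test cannot discriminate: its outcome contains no placebo information.

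Fourth, the contrast is weaker for the fMRI mediators on which the plan bases its power, and a half-specific pathway is usually missed. That stands as a cost.

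**Conclusion.** The concern holds, as an improvement the plan should make and not as a failure to test its hypothesis. The alcohol-session mediation cannot distinguish a general from an alcohol-specific brain pathway. The contrast can, with the power shown above, under assumed path sizes, session correlation and a two-sided alpha of .05. The comparison between pathways is the informative result, not the absolute percentages. Confidence is medium, because part of the analysis text and Figure 8 cannot be read.

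**What to change.** - Keep the alcohol-session mediation as the test of Hypothesis 4.
- Pre-specify a second mediation with the alcohol-minus-placebo difference in noise-blast volume as outcome and session order as a covariate. State which session's DTI and T1 scans are used.
- For task-fMRI mediators, use both sessions: bootstrap the difference between the two sessions' indirect effects, or use the matching mediator contrast. The matching contrast picks up an alcohol-specific a-path (76–80% of trials) but not an alcohol-specific b-path (about 2%), so the bootstrapped difference is the more general choice.
- Do not substitute adjustment for the placebo score, or pair an alcohol-session-only fMRI mediator with the difference outcome.
- Claim an alcohol-specific neural mechanism only if the contrast is significant. Otherwise report mediation of aggression after alcohol, and do not read a non-significant contrast as proof of a general pathway.
- State the contrast's power and the session correlation assumed. If Figure 8 already shows such a contrast, say so in the text.
- Reconcile the Session 2 sentence under MRI Sessions, which names the same Session 1 beverage for both alternatives, with the counterbalanced order; the contrast depends on the crossover.

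**Cost.** Analysis work only, at the planned sample size. At a session correlation of .3, power for an alcohol-specific pathway is 69%, and reaching 80% would take about 120–125 per group instead of 99. Participants who miss Session 2 have no difference score, and the allowance of 4 extra participants covers only exclusions for suspicion.

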#### Phase II - Investigating Neural Mechanisms in an S4S Sub-Sample

[figure not shown]
Participants. From the 2018-2020 cohorts of the S4S sample, I will recruit [202] individuals with low ( $N = 101$ ) and high ( $N = 101$ ) polygenic risk scores for alcohol-influenced aggression for a brain imaging experiment. Participants [will be equal numbers of males and females and] are expected to reflect the ethnic/racial makeup of the larger S4S sample which is relatively diverse (40% male, 60% female; 51% White, 19% African American, 15% Asian, 6% Hispanic/Latino, and 9% other/multiracial/unknown). Ages will range from 21-35 to ensure that only adults complete the study, that they can legally consume alcohol, and that aging effects do not influence our MRI data.

Recruitment and Screening. I will recruit VCU students who enrolled in the 2018-2020 cohorts of the S4S study, using their existing contact information in the S4S participant database. Participants will be recruited based on their polygenic risk scores that were obtained from the [discovery] GWAS. The S4S GWAS will not be used to establish the polygenic risk scores used to recruit these participants as they draw from the same pool of individuals. Establishing polygenic effects on behavior requires replication in an independent sample, as the use of dependent samples artificially inflates association statistics. Recruitment based on polygenic risk scores will proceed by contacting individuals from the lowest end of the distribution of polygenic risk scores (low risk group) and the highest end of the distribution of risk scores (high risk group), working from both ends of the distribution towards the median. Individuals who are contacted based on their risk scores will be screened with an online survey various conditions that would make the alcohol administration and MRI scanning procedures unsafe or invalid (see Protection of Human Subjects for a detailed list) and will be contacted to schedule an appointment if they pass these criteria.

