#### Potential Problems and Alternative Strategies

Participants in the low and high polygenic risk groups will likely differ on other variables (e.g., physical health) that might serve as problematic confounds. To address this, participants from each group will be closely-matched on age, sex, race, and socioeconomic status. The groups will be equated in physical and mental health as the screening procedures exclude any individuals with diagnosed physical or mental pathologies. There are also risks posed by the MRI environment, alcohol administration, and aggression task procedures. I have extensive MRI experience, participants undergo extensive screening procedures, and participants are under constant supervision by CARI center staff who are certified in safe MRI and alcohol administration procedures. CARI center staff are prepared to effectively handle any potential medical emergencies. If a brain abnormality is observed, a licensed radiologist is available through the CARI facility for consultation. The success of this study hinges on effective participant recruitment. Multiple offshoot studies using S4S data have been successful (e.g., an F31-funded fMRI study in [name] lab that recruits S4S participants for based on polygenic risk scores for externalizing behaviors). Further, the recruitment pool is large enough to provide many potential participants who meet this study's inclusionary criteria.

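### The visible mediation plan names no covariates, and matching the risk groups does not protect the brain-to-aggression path, so the indirect-effect test can be falsely positive

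*Combined protocol and SAP*

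**What the plan says.** The Phase II Analytic Plan (the text after the Figure 6 caption) sets up models in which "the effect of polygenic risk score group on aggression (after the alcohol administration) will be mediated by functional and structural brain estimates". The mediators come "from brain regions that were significantly different between the two polygenic risk groups". The indirect effect is tested in the PROCESS macro "using 5,000 bootstrapped resamples". These sentences are complete and mention no covariate. By contrast, the GCTA plan lists age, ethnicity/race, sex and socioeconomic status as fixed-effect covariates, and the GWAS plan includes demographic covariates.

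Confounding in Phase II is taken up under Potential Problems and Alternative Strategies, and only as a difference between the two risk groups. The remedy there is that "participants from each group will be closely-matched on age, sex, race, and socioeconomic status", together with the statement that "the screening procedures exclude any individuals with diagnosed physical or mental pathologies". The Participants paragraph adds a sample of "equal numbers of males and females", of mixed race and ethnicity. Under MRI Sessions, the alcohol dose is scaled by sex "due to sex differences in body fat composition and alcohol metabolism", and opponents are presented as being of the participant's own sex.

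**The concern.** An indirect effect is the product of two paths: group to brain (a) and brain to aggression given group (b). Matching makes sex, age, race and socioeconomic status independent of risk group. That protects a and the total group effect on aggression. It does nothing for b, which is estimated from differences between people within the groups, who still vary on these factors. A factor that shifts both the brain measure and the noise-blast volume produces a non-zero b even when the brain measure plays no part in aggression.

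The way mediators are chosen makes this matter more. Only regions that already differ by group go forward, so a is non-zero in the sample by selection and the bootstrap becomes largely a test of b, the path that matching leaves open. Carrying the matched pairs into the model could protect b, but the mediation text describes no pair term. What is at stake is that a region could be reported as a neural mechanism of polygenic risk when it only tracks sex or another demographic factor.

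**Working it through.** **Inputs from the documents.** Analysable sample 198, 99 per group (Phase II power analysis); sexes equally represented; mediators limited to regions that differ by group; bootstrap test of the indirect effect.

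**Assumptions, none given in the documents.** Two-sided 95% interval; group difference in the mediator a = 0.6 SD, or 0.4 SD as a variant; true b = 0; direct group effect on aggression 0.3 SD; sex shifts the mediator by dM and aggression by dY, in residual SDs. Sex stands in for any shared factor.

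**The plan's own figure.** 198 + 4 expected exclusions = 202, as stated. The basis of 198 cannot be reproduced. The target indirect effect of 0.09% has no clear unit, and the path coefficients, SD and alpha are not given. Read as variance explained, it would need (1.960 + 0.842)² × (1 − 0.0009)/0.0009 ≈ 8,713 participants. Read as a product 0.3 × 0.3 = 0.09, a Sobel calculation gives about 167 to 174. This does not show 198 to be wrong, and nothing below depends on it.

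**Closed form.** With sex balanced across groups, its variance within groups is 1/4. When true b = 0 and sex is omitted:

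- the estimate of b tends to (dM·dY/4)/(1 + dM²/4);
- the induced correlation is r = (dM·dY/4)/√[(1 + dM²/4)(1 + dY²/4)];
- z = r√195/√(1 − r²), where 195 = 198 − 3 fitted terms;
- the rejection rate is Φ(z − 1.96) + Φ(−z − 1.96).

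For dM = dY = 0.5: 0.0625/1.0625 = 0.059, z = 0.82, rejection 13%.

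| dM / dY (SD) | Limit of b | r | z | b-path rejected |
|---|---|---|---|---|
| 0.3 / 0.3 | 0.022 | 0.022 | 0.31 | 6% |
| 0.5 / 0.5 | 0.059 | 0.059 | 0.82 | 13% |
| 0.8 / 0.5 | 0.086 | 0.090 | 1.26 | 24% |
| 0.8 / 0.8 | 0.138 | 0.138 | 1.94 | 49% |

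A 40:60 sex mix, which the same paragraph also mentions, would replace 0.25 by 0.24 and change little.

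**Simulation of the indirect-effect test.** Percentile bootstrap, 2,000 trials of 1,000 resamples, true b = 0:

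| a (SD) | dM / dY (SD) | No covariate | Sex as covariate |
|---|---|---|---|
| 0.6 | 0 / 0 | 5.3% | 5.0% |
| 0.6 | 0.3 / 0.3 | 7.1% | 6.3% |
| 0.6 | 0.5 / 0.5 | 13.7% | 6.0% |
| 0.6 | 0.8 / 0.5 | 23.9% | 4.5% |
| 0.6 | 0.8 / 0.8 | 51.2% | 4.9% |
| 0.4 | 0.5 / 0.5 | 9.5% | 4.4% |
| 0.4 | 0.8 / 0.8 | 36.1% | 3.5% |

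The simulation standard error near 5% is √(0.05 × 0.95/2000) ≈ 0.5 points, so at 0.3 SD the gain from adjustment is barely distinguishable. A smaller bootstrap run with no direct effect gave 13%, 23% and 53% for the 0.5/0.5, 0.8/0.5 and 0.8/0.8 cases.

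The 0.4 SD rates are lower largely because fewer regions pass the group-difference screen (about 75-77%, against 98-99% at 0.6 SD). Among regions that pass, they are 12.2% and 47.5%. The screen in the simulation was a single t-test, simpler than the plan's imaging threshold.

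**Checks (600 trials each).** Sex affecting only the mediator, or only aggression: 6.0% each, within simulation error of 5%. No group difference (a = 0) with 0.8/0.8: 1.5% overall. Inflation therefore needs both a shared factor and a real or screened-in group difference.

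**The case against.** Three stronger readings are tempting, and the documents do not support them.

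**That the plan adjusts for nothing.** The Phase II Analytic Plan is broken in the copy reviewed. The sentence on the behavioural model stops part-way, the imaging text resumes part-way, citations 47 to 53 appear nowhere, and Figure 8, which depicts the mediation models, is not shown. Covariates may have been stated there. What can be said is that the mediation sentences, which are intact, name none. For the same reason nothing can be said about covariates in the behavioural comparison of the groups.

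**That Hypothesis 4 would be declared supported at these rates.** Hypothesis 4 also requires higher risk scores to go with greater laboratory aggression, which the behavioural model tests separately. Requiring a significant positive group effect as well as a false mediator brings the rate to about 1% or less if group has no effect on aggression. With a 0.3 SD direct effect it is about half the tabulated rate: near 7% at 0.5/0.5 and about a quarter at 0.8/0.8. The visible text does not make mediation conditional on the behavioural result, so a false claim about a single region remains possible.

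**That the plan itself shows sex to be a confounder.** Scaling the dose by sex is a design control, a fixed sex ratio is not evidence of confounding, and same-sex opponents imply neither a direction nor a size. Sex is a plausible shared factor, not a demonstrated one.

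It is also fair that "Ages will range from 21-35" and health screening narrow confounding by age and diagnosed illness. They do not remove variation in sex, race or socioeconomic status, and none of these objections restores protection to the brain-to-aggression path.

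**Conclusion.** The concern holds in this limited form. The mediation models, as far as they can be read, name no covariates, and the stated safeguard does not reach one of the two paths that make up the indirect effect. Under the assumptions above, the test is close to nominal if the shared factor shifts both variables by 0.3 SD, has between two and three times the nominal error at 0.5 SD, and fails about half the time at 0.8 SD. These rates apply to the indirect-effect test for a region that differs by group, not to Hypothesis 4 as a whole. The documents supply none of the effect sizes, so the direction of the problem is established and its size in this study is not. The change is still worth making, because it is nearly free and the mechanism claim rests on this model.

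**What to change.** In the mediation paragraph of the Phase II Analytic Plan, state that sex, age, race/ancestry and socioeconomic status enter as covariates in both the mediator equation and the outcome equation of every PROCESS model. If covariates were already intended, this sentence makes them explicit.

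The variables must be collected for matching anyway, so no new data are needed. The cost is about seven degrees of freedom out of 198: one each for sex, age and socioeconomic status, and four for the five race/ethnicity categories listed for the sample. In simulation with a true mediator (a = 0.4, b = 0.2) and no sex effect, power was 62.5% without and 62.3% with sex as covariate; the other three variables were not simulated.

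The plan should also acknowledge that mediator-outcome confounders outside these four variables remain, as a limit on the mechanism claim. A sensitivity analysis for such unmeasured confounding would be a useful addition.
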